5.10.4. Vital Signs and Body Weight

Vital signs and weight will be summarized by treatment group and visit. Change from baseline (last nonmissing value up to Visit 3) to postbaseline value for vital signs and weight will be summarized by treatment group and visit for patients who have both a baseline and at least 1 postbaseline result.

Treatment differences in mean change will be assessed using MMRM. The MMRM model will be used for the analysis during the treatment period and will contain the terms for treatment, baseline value, visit, and visit-by-treatment interaction as factors; patient as random effect; and CS as the variance-covariance structure. Only scheduled measures will be included in the MMRM analyses.

An analysis of covariance (ANCOVA) will also be conducted for the last nonmissing values during the study including the safety follow-up visit for the Safety Population. The ANCOVA model will use treatment, baseline value of the dependent variable as covariates.

The percentages of patients with treatment-emergent high or low vital signs at any time after randomization will be summarized and compared between treatment groups using Fisher's exact test. A treatment-emergent high result is defined as a change from a value less than or equal to the high limit (140 mm Hg for systolic blood pressure, 90 mm Hg for diastolic blood pressure, and 100 bpm for pulse) at baseline to a value greater than the high limit at any time that meets the specified change criteria after randomization. A treatment-emergent low result is defined as a change from a value greater than or equal to the low limit (90 mm Hg for systolic blood pressure, 50 mm Hg for diastolic blood pressure, and 50 bpm for pulse) at baseline to a value less than the low limit at any time that meets the specified change criteria after randomization. Patients with missing baseline measures will be excluded from this analysis unless otherwise specified. Scheduled visits, unscheduled visits, and retest measurements will be included in this analysis. [Table BDCP.3](#) will be used to define the low and high limits and change thresholds.

Table BDCP.3. Categorical Criteria for Abnormal Treatment-Emergent Blood Pressure and Pulse Measurement

Parameter	Low	High
Systolic BP (mm Hg) (Supine or sitting)	≤ 90 and decrease from baseline ≥ 20	≥ 140 and increase from baseline ≥ 20
Diastolic BP (mm Hg) (Supine or sitting)	≤ 50 and decrease from baseline ≥ 10	≥ 90 and increase from baseline ≥ 10
Pulse (bpm) (Supine or sitting)	<50 and decrease from baseline ≥ 15	>100 and increase from baseline ≥ 15

Abbreviations: BP = blood pressure; bpm = beats per minute; mm Hg = millimeters of mercury.

5.10.5. Laboratory Measures

The data from laboratory testing will be summarized by treatment group and visit. Change from baseline (last nonmissing value up to Visit 3) to postbaseline value for laboratory tests (except for FSG, HbA1c, and Antibody) will be summarized for patients who have both a baseline and at least 1 postbaseline result. Treatment differences in mean change for these laboratory tests will be evaluated using MMRM model. The MMRM model will be used for the analysis during the treatment period and will contain the term for treatment, baseline value, visit, and visit-by-treatment interaction as factors, patient as random effect, and compound symmetric as the variance-covariance structure. Analyses will be provided in both international units (SI) and conventional units (CN). The MMRM analysis will only include lab tests for the scheduled visits specified in the protocol. For some selected laboratory measures, log-transformed value will be

used in MMRM when necessary, and the geometric LS means as well as the percentage change from baseline will be reported.

The last nonmissing values during the study including the safety follow-up visit for the Safety Population will also be analyzed by an ANCOVA model. The ANCOVA model will use treatment, baseline value of the dependent variable as covariates. For some selected laboratory measures, log-transformed value will be used in the ANCOVA model.

The percentages of patients with treatment-emergent abnormal laboratory results at any time after randomization (including the treatment period and follow-up period) will be summarized and compared between treatment groups using Fisher's exact test. A treatment-emergent abnormal result is defined as a change from normal at baseline to abnormal at any time after randomization. Covance reference ranges will generally be used to define the low and high limits. Patients with missing baseline lab measures will be excluded from this analysis unless otherwise specified. Scheduled visits, unscheduled visits, and retest measurements will be included in this analysis.

A lab listing in the Safety Population who had a treatment-emergent abnormal laboratory value during the study will be provided, including the actual measurement, abnormal result, and reference low or high limits.

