9.4.6.4. Laboratory Measures

Summary statistics will be provided for laboratory measures by treatment group and by visit. An additional listing will be presented for all laboratory measurements that are outside the normal range.

Descriptive statistics for the laboratory analyses will be presented by treatment group and visit. Laboratory analyses with categorical responses will be summarized by visit and treatment group using frequency and percentage.

The maximum/minimum post-baseline observation (as applicable for a lab) will be compared to the baseline observation by examining the proportion of participants whose test values are within and outside the reference ranges.

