(defined as the observed data with collection date before or on the last dose date +10 days). Sensitivity analyses for selected efficacy measures may be conducted on the Randomized Population using the data up to the study treatment discontinuation.

Unless otherwise stated, the safety analyses will be conducted on the safety analyses set based on the Safety Population using all data collected during the study including treatment and follow-up period regardless of the treatment disposition status. The safety measures will be summarized and compared between LY3209590 (by pooling LY3209590 Algorithm 1 and LY3209590 Algorithm 2 data) and insulin degludec. Safety parameters derived from CGM measures will be summarized and compared between LY3209590 Algorithm 1 and degludec.

Unless otherwise specified, the baseline value used for the analyses will be the last non-missing value obtained for each participant prior to or on the date of first study IP dose (or randomization visit date if first dose date is missing). The baseline liver enzyme lab measures will be the average of all assessments prior to and at randomization visit.

All tests of treatment effects will be conducted at a 2-sided alpha level of 0.1, unless otherwise stated, and all confidence intervals (CIs) will be given at a 2-sided 90% level.

Puerto Rico and the United States (US) are always pooled in the analysis, as Puerto Rico will be considered part of US during randomization. All analyses using country in the model will use pooled country, unless otherwise specified. No other pooling of countries is needed.

For continuous measurements, summary statistics will include sample size, mean, median, standard deviation (SD), minimum, and maximum. For certain variables that are considered to be log-normally distributed, the geometric mean and coefficient of variation (CV) will be provided instead.

For categorical measurements, summary statistics will include sample size, frequency, and percentage. Fisher's exact test will be used. Chi-squared test will be used for multi-category variables.

A mixed-model repeated measures (MMRM) model will be used for continuous outcomes with repeated postbaseline measurements to compare treatment arms, unless otherwise noted.

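### The treatment-emergent abnormal laboratory result in SAP 5.10.5 has no direction and no at-risk denominator; defining high and low separately is a cheap improvement

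*SAP*

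**What the plan says.** SAP 5.10.5 compares the arms on the percentage of participants with a treatment-emergent abnormal laboratory result, using Fisher's exact test. The event is defined once for all tests: "A treatment-emergent abnormal result is defined as a change from normal at baseline to abnormal at any time after randomization". The limits come from the laboratory: "Covance reference ranges will generally be used to define the low and high limits". The one stated exclusion is: "Patients with missing baseline lab measures will be excluded from this analysis unless otherwise specified". The section asks for at least one postbaseline result in the change-from-baseline summaries, but does not repeat that condition for this percentage.

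SAP 5.10.4 handles vital signs differently. It has a high event, "A treatment-emergent high result is defined as a change from a value less than or equal to the high limit", and a separate low event, "A treatment-emergent low result is defined as a change from a value greater than or equal to the low limit". Each names the baseline side from which the event can arise. Its stated exclusion, however, is also only a missing baseline.

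Protocol 9.4.6.4 gives a related laboratory summary: "The maximum/minimum post-baseline observation (as applicable for a lab) will be compared to the baseline observation". It uses the extreme suited to the test, but then sorts values only into inside or outside the reference range.

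For the significance level, SAP 5.1 states: "All tests of treatment effects will be conducted at a 2-sided alpha level of 0.1".

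**The concern.** A reference range has two ends, and for tests such as potassium, sodium or calcium each end can matter. An event defined only as leaving the range treats both ends alike. Three things follow from the wording of 5.10.5:

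- Low and high results fall into the same count.
- A participant who moves from low to high, or from high to low, is never counted, because the baseline was not normal.
- A participant abnormal at baseline cannot have the event but is not removed, so he or she enters the percentage as a non-event.

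Clinical laboratory results are an exploratory endpoint in Protocol section 3 and SAP 4.3, and this is the general categorical comparison between arms for them. At stake is whether the table can show a one-sided excess, and whether its percentages describe the people who could have had the event.

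**Working it through.** **Inputs from the documents.** About 119 participants per arm (Protocol 9.2), Fisher's exact test (SAP 5.10.5), and two-sided alpha of 0.10 (SAP 5.1). Neither document gives a planning figure for the laboratory analysis, so there is none to reproduce. Event rates and baseline-abnormal fractions below are assumptions. The safety comparison also adds the former Algorithm 2 participants to the LY3209590 group (SAP 5.10); their number is not given, so 119 per arm is a round basis.

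**Step 1, combining directions.** If everyone is normal at baseline and each participant has at most one kind of event, combined rate = low rate + high rate. Exact power of Fisher's test was obtained by summing binomial probabilities over all tables with p ≤ 0.10, at 119 per arm.

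| Low, arm A vs B | High, arm A vs B | Combined | Power, low alone | Power, combined |
|---|---|---|---|---|
| 15% vs 5% | 5% vs 5% | 20% vs 10% | 0.79 | 0.64 |
| 15% vs 5% | 5% vs 10% | 20% vs 15% | 0.79 | 0.22 |
| 15% vs 5% | 5% vs 15% | 20% vs 20% | 0.79 | 0.07 |

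The first row is the plain one-direction effect: power is lost but the effect is not cancelled. Only the last row, with mirrored effects, removes the signal.

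The same pattern in counts, out of 119 per arm:
- Low 10 vs 2: p = 0.034.
- Adding 2 high events in each arm gives 12 vs 4: p = 0.067, still below 0.10.
- Adding high events of 2 vs 10 gives 12 vs 12: p = 1.0.

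**Step 2, the denominator.** Let q be the fraction abnormal at baseline and r the event rate among those normal at baseline. Under the written rule, reported percentage = r × (1 − q). For r = 20%:
- q = 10%: 20% × 0.9 = 18%
- q = 50%: 20% × 0.5 = 10%

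If q is equal in both arms, the risk difference shrinks by the same factor and the risk ratio does not change. Worked counts with 119 per arm:

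| q (both arms) | At risk per arm | Events | At-risk % | Reported % | Risk difference | Fisher p, at risk vs as written |
|---|---|---|---|---|---|---|
| about 20% | 95 | 19 vs 10 | 20.0 vs 10.5 | 16.0 vs 8.4 | 9.5 → 7.6 points | 0.105 vs 0.112 |
| about 40% | 71 | 14 vs 7 | 19.7 vs 9.9 | 11.8 vs 5.9 | 9.9 → 5.9 points | 0.155 vs 0.169 |

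If q differs, say 30% vs 40%, an equal true rate of 20% is reported as 20% × 0.7 = 14% vs 20% × 0.6 = 12%. In counts this is about 17 vs 14 of 119, p = 0.70. The percentages separate without cause, but no false signal follows.

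**The case against.** A reader might infer that the SAP orders low and high to be pooled, so that real effects will cancel. The documents do not support that. Pooling is the literal result of a definition without direction, but no sentence says the two are combined. The section refers to low and high limits, and its listing is to show them. A programmer could split the directions, although nothing prespecifies it. Full cancellation also requires one analyte to move opposite ways in the two arms, and no figure in the documents suggests this.

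A second tempting inference is that a laboratory shift would go unseen. The plan has other routes to it. SAP 5.10.5 also compares signed change by MMRM and the last value, follow-up included, by ANCOVA. Both keep direction, and mirrored shifts are what a comparison of means tends to detect. The listing gives each abnormal value with its limits, and Protocol 9.4.6.4 lists every out-of-range result. SAP 5.10.5.2 analyses elevations of ALT, AST, bilirubin and ALP on their own, by baseline category, so liver enzymes are not a good example of the gap.

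A third is that the denominator distorts the test. With balanced baselines it barely does, as Step 2 shows. Nor is Protocol 9.4.6.4 a better model, since it too reports only inside or outside the range.

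What remains is narrower. Models of means do not count excursions beyond a limit, the MMRM uses scheduled visits only, and the listings make no comparison. The categorical table is the place for that comparison. As worded, it is less exact than the vital-sign rule one section earlier, and no reason is given for the difference.

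**Conclusion.** The point holds as a minor weakness in an exploratory safety table. Taken literally, 5.10.5 merges two directions, misses shifts across the range, and leaves participants who cannot have the event in the percentage. Under the assumed rates, a one-direction effect loses power from 0.79 to 0.64; complete masking is confined to opposite movements between arms. Percentages and risk differences are too small by the fraction abnormal at baseline, while the risk ratio and p-value are nearly unchanged when that fraction is balanced. These sizes rest on assumed event rates, assumed baseline fractions and 119 per arm. The primary HbA1c analysis, the sample size and the noninferiority conclusion are not touched.

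**What to change.** In SAP 5.10.5, replace the single event with two per analyte:

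- **Treatment-emergent high:** baseline at or below the upper limit, and any later value above it.
- **Treatment-emergent low:** baseline at or above the lower limit, and any later value below it.

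This follows the direction-specific pattern of 5.10.4. It also captures low-to-high and high-to-low shifts, because a low baseline is at risk for high and a high baseline is at risk for low.

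For each event, use as denominator the participants whose baseline puts them at risk for that direction and who have at least one postbaseline value. Apply the same denominator to the vital-sign percentages in 5.10.4, where the stated exclusion is likewise only a missing baseline.

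The cost is a wording change and two flags per analyte instead of one. The table becomes longer, and denominators will differ between analytes and directions. No new data are needed.

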5.10.5.1. Lipid Measures

Triglycerides, total cholesterol, LDL-C, and HDL-C (results from fasting samples) will take log-transformation before being analyzed by MMRM model defined above for the Safety Population. The last nonmissing measurements will also be log-transformed and analyzed by the previously defined ANCOVA model.

A listing of patients with postbaseline fasting triglyceride value ≥ 400 mg/dL or non-fasting triglycerides > 600 will be provided (scheduled visits, unscheduled visits, and repeat measurements will be included).

5.10.5.2. Liver Enzyme Elevation Measures

The liver enzymes and biomarkers (alanine aminotransferase [ALT], aspartate aminotransferase [AST], Alkaline phosphatase [ALP], total bilirubin [TBL] and Gamma glutamyl transferase [GGT]) will take log-transformation before performing the MMRM and ANCOVA analyses. In addition, the percentage of patients with the following elevations in liver enzymes at any postbaseline visit after randomization including the treatment period and post-treatment follow-up period will be summarized for subsets based on baseline categories.

- The analysis of any postbaseline ALT (AST) ≥ 3 -fold (3X) ULN will contain 4 baseline subsets:
 - patients whose non-missing maximum baseline value is less than or equal to 1X ULN,
 - patients whose maximum baseline is greater than 1X ULN but less than 3X ULN,

- patients whose maximum baseline value is greater than or equal 3X ULN, and
- patients whose baseline values are missing.
- The analysis of any postbaseline ALT (AST) $\geq 5X$ ULN will be contain 5 baseline subsets:
 - patients whose non-missing maximum baseline value is less than or equal to 1X ULN,
 - patients whose maximum baseline is greater than 1X ULN but less than 3X ULN,
 - patients whose maximum baseline is greater than or equal to 3X ULN but less than 5X ULN,
 - patients whose maximum baseline value is greater than or equal to 5X ULN, and
 - patients whose baseline values are missing.
- The analysis of any postbaseline ALT (AST) $\geq 10X$ ULN will contain 6 baseline subsets:
 - patients whose non-missing maximum baseline value is less than or equal to 1X ULN,
 - patients whose maximum baseline is greater than 1X ULN but less than 3X ULN,
 - patients whose maximum baseline is greater than or equal to 3X ULN but less than 5X ULN,
 - patients whose maximum baseline is greater than or equal to 5X ULN but less than 10X ULN,
 - patients whose maximum baseline value is greater than or equal to 10X ULN, and
 - patients whose baseline values are missing.
- The analysis of any postbaseline total bilirubin $\geq 2X$ ULN will contain 4 baseline subsets:
 - patients whose non-missing maximum baseline value is less than or equal to 1X ULN,
 - patients whose maximum baseline is greater than 1X ULN but less than 2X ULN,
 - patients whose maximum baseline value is greater than or equal to 2X ULN, and
 - patients whose baseline values are missing.
- The analysis of any postbaseline ALP $\geq 2X$ ULN will contain 4 baseline subsets the same as above for total bilirubin

For the above elevation analysis, maximum baseline and maximum postbaseline will be used. Maximum baseline is defined as the maximum non-missing observation in the baseline period. The maximum postbaseline is defined as the maximum non-missing postbaseline measurements including scheduled, unscheduled and retest measurements.

A listing of patients with any post randomization

- elevation of serum ALT to ≥ 5 -fold ULN on 2 or more consecutive blood tests
- elevated serum TBL to ≥ 2 -fold ULN (except for cases of known Gilbert's syndrome)
- elevation of serum ALP to ≥ 2 -fold ULN on 2 or more consecutive blood tests
- study participant discontinued from treatment due to a hepatic event
- hepatic event considered to be an SAE

will be provided, including demographics, disposition, study drug exposure, AEs, concomitant medications, all the liver measurements (ALT, AST, total bilirubin, ALP and GGT). The time course plot of ALT, AST, ALP, TBL and GGT will also be provided for the patients meeting the above criteria.

5.10.6. *Electrocardiograms*

Electrocardiograms will be collected at specific study visits. For Visit 3, 6, 9, 15 and 17, a triplicate ECG will be collected. The other visits, a single ECG will be collected. The average values will be used in the analysis.

The actual and change from baseline for selected ECG parameters (heart rate and intervals) will be analyzed using the MMRM model. The MMRM model will be used for the analysis during the treatment period and will contain the term for treatment, baseline value, visit, and visit-by-treatment interaction as factors, patient as random effect, and compound symmetric as the variance-covariance structure. The last nonmissing measurements will also be analyzed by the ANCOVA model with treatment and baseline value as covariates.

5.10.7. *Immunogenicity*

The sample to determine antibody against LY3209590 will be collected at protocol-specified visits. Treatment emergent anti-drug antibodies (TEADA) can be subclassified as either treatment induced (baseline antibody level is not detected) or treatment boosted (baseline antibody level is detected):

- treatment induced response: a postbaseline titer ≥ 2 -fold of the minimum required dilution (1:20) if the baseline status is not detected (i.e., titer less than the minimum required dilution)
- treatment boosted response: a postbaseline titer ≥ 4 -fold of the baseline titer if the baseline status is detected. For an example, 1:20 at baseline and 1:80 postbaseline is treatment boosted.

The frequency and percentage of a participant's baseline ADA status for patients with baseline and at least one postbaseline measurement, allowing TEADA evaluation, will be summarized.

The TEADA status will be determined by all postbaseline data. The number and percentage of patients with positive TEADA response any time after randomization including the treatment period and follow-up period will be summarized by treatment group.

A listing of anti-LY3209590 antibodies at each visit will be provided for the Safety Population. The listing will include anti-LY3209590 antibody status (detected/not detected), the titer for detected samples and the TEADA status.

5.11. Continuous Glucose Monitoring Analysis

5.11.1. General Consideration

For all study participants meeting study entry criteria, a CGM device will be inserted and activated at (Visit 2). Patients will be unblinded to the CGM system and wear the study provided CGM during the study duration.

All participants who are randomized to either LY3209590 Algorithm 1 or insulin degludec, receive at least 1 dose of study treatment, and have evaluable CGM data from baseline and at least 1 postbaseline will be included in the analyses. The data collected after permanent discontinuation of the IP will be censored. There will be no multiplicity adjustment. Additional analysis may be conducted to compare between the LY3209590 (by pooling LY3209590 Algorithm 1 and LY3209590 Algorithm 2) and insulin degludec if deemed necessary.

According to the 2020 American Diabetes Association standard of medical care in diabetes, the CGM data will be included in the analysis only if at least 70% of the total measures in the analysis period are obtained (defined as a valid CGM period). For example, the 24-hour period will have 288 measures and the minimum number of measures will be 202. All the CGM derivations are based on the data from valid CGM period unless otherwise specified.

The CGM variables will be derived for each CGM day when the analysis data meet the above requirement. The derived variables for a visit will be based on the daily CGM variables within the given visit. Also, the CGM variables will be derived for the following analysis periods: baseline (using data prior to the first dose date), 0-12 Week, 12-26 Week and 0-26 Week of treatment period.

Summary statistics will include the number of observations, mean, median, maximum, minimum, and SD for all continuous measures. For categorical measures, the number of observations, proportion, and frequency will be included in summary statistics. All analyses will be performed by visit and treatment.

